5. STUDY TREATMENT

5.1. Study Drug Administration

Please note: at any timepoint where futibatinib and pembrolizumab are administered on the same day, pembrolizumab should be administered prior to futibatinib if possible. A study cycle is defined as 21 days.

5.1.1. Futibatinib

Futibatinib is supplied as 4 mg tablets and will be taken orally at a dose of 20 mg daily until the patient meets any of the administration discontinuation criteria (see [Section 4.4](#)).

Futibatinib should be administered under fasting conditions. It should be taken with a glass of water, on an empty stomach, at approximately the same time each day. No food should be consumed for 2 hours prior and 1 hour after the dose of futibatinib, but patients may drink water during this period.

In the event of a dosing delay up to 12 hours after the scheduled dosing time, the patient should still take that day's dose. If the dosing delay continues for >12 hours after the scheduled dosing time, or if the patient vomits after a dose, the patient should skip dosing for that day and not make up for it the following day.

5.1.2. Pembrolizumab

Pembrolizumab is administered as an I.V. infusion of 200 mg on Day 1 of each cycle (that is, every 3 weeks). Treatment continues for a maximum of 35 doses or a maximum duration of 2 years (whichever is earlier), or until the patient meets any of the administration discontinuation criteria (see [Section 4.4](#)).

Pembrolizumab should be administered according to the instructions on the approved product label.

5.2. Definition of Dose-Limiting Toxicity

For this study, unacceptable toxicity will include any event meeting the criteria for dose-limiting toxicity (DLT), as outlined below. An adverse event not meeting the criteria for a DLT may also be considered an unacceptable toxicity, if it is not tolerable in the long-term and necessitates discontinuation of one or more elements of the combination therapy.

DLT Definition

All toxicities will be graded using the National Cancer Institute – Common Terminology Criteria for Adverse Events (NCI-CTCAE) Version 5.0, based on Investigator assessment. The occurrence of any of the following toxicities during Cycle 1 will be considered a DLT, if assessed by the Investigator to be related to study treatment administration.

- Grade 4 nonhematologic toxicity (not laboratory)
- Grade 4 neutropenia lasting >5 days
- Grade 4 thrombocytopenia of any duration

- Grade 3 thrombocytopenia associated with clinically significant bleeding
- Any nonhematologic AE \geq Grade 3 in severity, with the following exceptions:
 - Grade 3 fatigue lasting \leq 3 days;
 - Grade 3 diarrhea, nausea, or vomiting without use of anti-emetics or anti-diarrheals per standard of care;
 - Grade 3 rash without use of corticosteroids or anti-inflammatory agents per standard of care.
- Any Grade 3 or Grade 4 nonhematologic laboratory value if:
 - Clinically significant medical intervention is required to treat the patient, or
 - The abnormality leads to hospitalization, or
 - The abnormality does not recover to Grade \leq 1 within 48 hours despite best supportive care, or
 - The abnormality results in a drug induced liver injury
 - Exceptions: clinically nonsignificant, treatable, or reversible laboratory abnormalities including liver function tests, uric acid, hyperphosphatemia, etc.
- Febrile neutropenia Grade 3 or Grade 4:
 - Grade 3 is defined as ANC $<1000/\text{mm}^3$ with a single temperature of $>38.3^\circ\text{C}$ (101°F) or a sustained temperature of $\geq38^\circ\text{C}$ (100.4°F) for more than 1 hour
 - Grade 4 is defined as ANC $<1000/\text{mm}^3$ with a single temperature of $>38.3^\circ\text{C}$ (101°F) or a sustained temperature of $\geq38^\circ\text{C}$ (100.4°F) for more than 1 hour, with life-threatening consequences and urgent intervention indicated.
- Grade 3 or higher visual impairment
- Prolonged delay (>2 weeks) in initiating Cycle 2 due to treatment-related toxicity
- Any treatment-related toxicity that causes the participant to discontinue treatment during Cycle 1
- Missing $>20\%$ of futibatinib doses as a result of drug-related AE(s) during Cycle 1
- Grade 5 toxicity

5.3. Dose and Schedule Modifications

5.3.1. Dose Modifications for Futibatinib

Stepwise dose reductions to 16 mg QD (first reduction) and 12 mg QD (second reduction) are permitted based on toxicities. If dose reduction fails to result in achieving the minimal criteria to resume treatment or, if toxicities occur which would necessitate reduction of the dose of futibatinib below 12 mg QD, the patient should be discontinued from futibatinib.

Following a dose reduction, if a benefit/risk assessment favors an increase of futibatinib dose up to the initial starting dose (20 mg QD, or 16 mg QD if this is determined as the recommended dose), an agreement with the Sponsor’s medical monitor is required prior to the dose increase.

If toxicities related to the dose reduction do not recover based on the criteria defined in the following sections within 21 days after the last dose of futibatinib, the patient will be discontinued permanently from treatment ([Section 4.4](#)). If resumption criteria are met within 21 days of the last dose of futibatinib, the patient may resume futibatinib treatment at the appropriate dose level.

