4.4. Discontinuation of Treatment

Pembrolizumab may be administered for a maximum of 35 doses or a maximum duration of 2 years, whichever is earlier. There is no maximum duration of futibatinib therapy. A patient will be discontinued from any or all study therapy for any of the following reasons:

1. Disease progression
2. Unacceptable AEs, or change in underlying condition such that the patient can no longer tolerate therapy, as evidenced by a dose delay > 21 days from the scheduled start date of the next cycle or need for more than 2 dose reductions outlined in this protocol. If such toxicity is associated with only 1 of the treatment components (futibatinib or pembrolizumab), the patient may discontinue that component and continue receiving the other if medically appropriate in the opinion of the Investigator.
3. Physician’s decision, including need for other anticancer therapy not specified in the protocol or surgery or radiotherapy to the only site(s) of disease being followed in the study
4. Pregnancy
5. Termination of the study by the Sponsor, or
6. At the patient’s request at any time irrespective of the reason.

Patients who withdraw consent for further treatment may choose to remain on study; in such a case, all study evaluations should continue as outlined in this protocol. If the patient withdraws consent to all follow-up assessments, the patient should be considered to have discontinued the study as described in [Section 4.5](#).

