5.3.1.1. Futibatinib Dose Modifications for Nonhematologic Toxicities

Dosing modification guidelines for nonhematologic and eye toxicities are provided in [Table 4](#) and [Table 5](#), respectively.

Table 4: Dose Modifications for Related Nonhematologic Toxicities

Grade	Dose Interruption/Resumption	Dose Adjustment
Grade 1 or 2	Maintain treatment at the same dose level	None
Grade 3	Withhold treatment until return to baseline or Grade ≤ 1	Reduce by 1 dose level from the previous level, except for Grade 3 nausea and/or vomiting controlled by aggressive antiemetic therapy or Grade 3 diarrhea responsive to antidiarrheal medication which does not require a dose hold or reduction.
Grade 4	Discontinue treatment	Permanent discontinuation of futibatinib.
Grade 4 (lab abnormality AE)	Withhold treatment until return to baseline or Grade ≤ 1	Futibatinib will be permanently discontinued if assessed by the Investigator as life threatening. If it is in the best interest of the patient to continue treatment in the opinion of the Investigator and after discussion with the Sponsor, the patient can continue treatment at a reduced dose level. However, futibatinib should first be held until toxicity returns to baseline or Grade ≤ 1 .

Abbreviations: AE=adverse event; ALT=alanine aminotransferase; AST=aspartate aminotransferase.

Note: Interrupt futibatinib if any toxicities are intolerable, regardless of the grade (including Grade 1 and 2). If or when the toxicity resolves to a tolerable state, consideration can be given to resuming futibatinib at the same dose if deemed appropriate or reduced by one dose level if needed.

Table 5: Dose Modifications for Related Eye Toxicities

Grade and Definition	Study Drug Management

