Grade 1	
If there is no evidence of eye toxicity on ophthalmologic examination, continue futibatinib therapy at the same dose level.
 
If diagnosis from ophthalmologic examination is keratitis or retinal abnormality such as central serous retinopathy (CSR)/ retinal pigment epithelial detachments (RPED), withhold futibatinib until signs and symptoms have resolved.
 
If toxicity is reversible (complete resolution or stabilization and asymptomatic) in 4 weeks according to ophthalmologic examination, resume futibatinib therapy at the next lower dose level after consultation with the medical monitor.
 
Monitor for recurrence every 1 to 2 weeks for a month and as clinically appropriate thereafter. If there is no recurrence then re-escalation can be considered in consultation with the medical monitor.^a

Grade 2	
Withhold futibatinib therapy.
 
If there is no evidence of drug-related corneal or retinal pathology on ophthalmologic examination, withhold futibatinib until signs and symptoms have resolved. Resume futibatinib therapy at the next lower dose level.
 
If diagnosis from ophthalmologic examination is keratitis or retinal abnormality, withhold futibatinib until signs and symptoms have resolved or stabilized.
 
If toxicity is Grade 2 and reversible (complete resolution or stabilization and asymptomatic) within 4 weeks according to ophthalmologic examination, resume futibatinib therapy at the next lower dose level after consultation with the medical monitor.

Grade 3	
If the toxicity is Grade 3, report as a serious adverse event and permanently discontinue futibatinib. If, however, the toxicity is Grade 3 and reversible (complete resolution or stabilization and asymptomatic) within 4 weeks and the subject is having clinical benefit, and the Investigator and the Sponsor's medical monitor agree that re-starting drug is in the best interest of the subject, then futibatinib therapy may be resumed at 2 dose levels lower if appropriate.^a Monitor for recurrence using appropriate investigations every 1 to 2 weeks for a month and as clinically appropriate thereafter.
 
For cases of recurrence consider permanent discontinuation.

Grade 4	
Permanently discontinue treatment with futibatinib.
 
Report as a serious adverse event and monitor resolution of the event until complete resolution, stabilization, or the subject is lost to follow-up or withdraws consent (which ever happens first).

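### Restarting futibatinib after eye toxicity: the 21-day limit in Protocol 5.3.1 contradicts the 4-week window in Table 5 for parts of Grades 1 and 2, with no stated precedence and no start for the 4 weeks

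*Protocol*

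**What the plan says.** Three places in the protocol limit how long futibatinib may be held before it must be stopped for good.

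- **Section 5.3.1 (general rule).** Toxicities must "recover based on the criteria defined in the following sections". If they do not do so "within 21 days after the last dose of futibatinib, the patient will be discontinued permanently from treatment". The next sentence is the mirror image: "If resumption criteria are met within 21 days of the last dose of futibatinib, the patient may resume futibatinib treatment".
- **Section 5.3.1.1 and Table 5 (eye toxicity).** This is the first section after the general rule, and it opens: "Dosing modification guidelines for nonhematologic and eye toxicities are provided in" Tables 4 and 5. For Grade 1 with keratitis or a retinal abnormality, Table 5 says: "If toxicity is reversible (complete resolution or stabilization and asymptomatic) in 4 weeks according to ophthalmologic examination, resume futibatinib therapy". For Grade 2 it says: "If toxicity is Grade 2 and reversible (complete resolution or stabilization and asymptomatic) within 4 weeks according to ophthalmologic examination, resume futibatinib therapy". In both cases the restart is one dose level lower, after consultation with the medical monitor. For Grade 3 the default is permanent discontinuation. Resumption two levels lower is possible if the event reverses within 4 weeks, the patient is benefiting, and the investigator and medical monitor agree. Grade 4 means permanent discontinuation.
- **Section 4.4 (cited by 5.3.1).** A patient stops for unacceptable adverse events "as evidenced by a dose delay > 21 days from the scheduled start date of the next cycle".

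The Note below Table 5 allows discretionary re-introduction for patients deriving benefit, with medical monitor agreement and re-consent. It does not mention the 21-day limit.

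**The concern.** Section 5.3.1 takes its recovery criteria from the sections that follow but sets the time limit itself, in mandatory terms and without an exception for eye toxicity. Table 5, inside those sections, has its own longer limit and does not say that it displaces the general one. A patient whose Grade 2 retinal event clears between the two limits must be taken off futibatinib permanently under one passage and restarted under the other.

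The first thing at stake is how a toxicity known for this drug class is handled. Two reporting consequences follow:

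- SAP 5.2.2 counts failure to follow the withdrawal criteria, and incorrect dosing, among important protocol deviations. A site that follows Table 5 could therefore be recorded as breaching 5.3.1.
- SAP 5.5.1.2 tabulates dose discontinuations, with reasons, by cohort and drug. With 20 to 26 patients per cohort, one patient classified differently moves that percentage by 1/26 = 3.8 to 1/20 = 5.0 points.

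**Working it through.** The plan gives no figure to reproduce. The check sets the passages side by side and does the calendar arithmetic.

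**1. The clocks**

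| Passage | Limit | Counted from |
|---|---|---|
| Protocol 5.3.1 | 21 days | last futibatinib dose |
| Protocol Table 5 | 4 weeks | not stated |
| Protocol 4.4 | more than 21 days | scheduled start of the next cycle |

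**2. Recovery after day 21 but within 4 weeks, by grade**

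| Eye toxicity | Section 5.3.1 | Table 5 | Opposed? |
|---|---|---|---|
| Grade 1, no evidence of eye toxicity on examination | not engaged (no hold) | continue | No |
| Grade 1, keratitis or retinal abnormality | stop permanently | resume | Yes |
| Grade 2, branch reversible in 4 weeks | stop permanently | resume | Yes |
| Grade 2, no drug-related corneal or retinal pathology | stop permanently | resume once resolved; this branch gives no time limit of its own | Unclear |
| Grade 3 | stop permanently | stop by default; may resume under conditions | Only where the exception is used |
| Grade 4 | stop permanently | stop permanently | No |

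**3. Length of the conflict if both clocks start at the last dose (assumption)**

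4 weeks × 7 = 28 days, and 28 − 21 = 7 days. The passages disagree for recovery on days 22 to 28.

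**4. Sensitivity to the start of the 4 weeks (assumption)**

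Suppose the 4 weeks run from onset and the last dose was taken s days after onset. Table 5's limit then falls 28 − s days after the last dose, and the overlap is (28 − s) − 21 = 7 − s days:

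- s = 0: 7 days
- s = 3: 4 days
- s = 6: 1 day
- s ≥ 7: none

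**5. Section 4.4 is not the same limit**

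Cycles last 21 days, so the next cycle is due on day 22, and the 4.4 limit is day 22 + 21 = 43. If the last dose was on cycle day d, that is 43 − d days after it:

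- d = 1: 42 days
- d = 15: 28 days
- d = 21: 22 days

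A 28-day hold stays within 4.4 when 43 − d ≥ 28, that is, d ≤ 15. It exceeds 4.4 for d = 16 to 21. It exceeds the 5.3.1 limit for every d, because 28 > 21. So 5.3.1 also disagrees with the section that it cites.

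**6. Can the window be reached?**

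Protocol 6.1 has retinal pigment epithelial detachment, a condition named in Table 5, monitored every 2 to 3 weeks. As an illustration, two-weekly checks from the start of a hold fall on days 14 and 28. Recovery could first be documented on day 28, at the end of a 4-week window counted from the last dose and beyond the 21-day limit.

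**The case against.** The best defence is that a toxicity-specific table with its own time limit naturally governs over a general paragraph. Section 5.3.1 does not name Table 5, and its sentence refers awkwardly to toxicities related to the dose reduction, which may narrow it. The Grade 1 and 2 restarts in question go through the medical monitor, Grade 3 needs the monitor's agreement, and the Note shows that re-introduction of the drug was contemplated. Protocol 1.3.2 reports ocular toxicity at low frequency in earlier futibatinib trials, and this study enrols about 46 patients.

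Much of this stands as a limit on size. It does not remove the contradiction. The specific-over-general reading is reasonable, but the protocol states no order of precedence. The Note depends on benefit and re-consent, whereas the Grade 1 and Grade 2 restarts in Table 5 do not.

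Four stronger readings are tempting, and the documents do not support them:

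- **Opposite instructions for three of the four grades over a fixed 7 days.** Directly opposed mandatory wording is confined to the two branches marked in the working, and the 7 days depend on a start date that Table 5 does not give.
- **Section 4.4 simply repeats the 21-day limit.** It uses another clock and is compatible with a 28-day hold when the last dose was on cycle days 1 to 15.
- **Sites will certainly diverge.** The monitor's role may produce uniform handling, so divergence is a risk and not a prediction.
- **The study's decision rules shift.** The primary response rule in SAP 5.4.1 uses best response up to progression or new anticancer treatment, not futibatinib discontinuation status. Protocol 5.2 lets an event that necessitates discontinuation count as unacceptable toxicity, so an individual case could bear on the 33% tolerability limit, but nothing shows that it would.

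**Conclusion.** The point holds: the protocol is wrong as written, an internal contradiction. Section 5.3.1 requires permanent discontinuation where Table 5 directs resumption, for Grade 1 eye toxicity with keratitis or retinal abnormality and for the reversible Grade 2 branch. For Grade 3 the clash arises only where the conditional permission is used, and Grade 4 is unaffected.

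The size is at most 7 days (recovery on days 22 to 28), on the assumption that Table 5's 4 weeks start at the last dose. It falls to 7 − s days, and to nothing at s ≥ 7, if they start at onset. The undefined start is itself a defect, and the different clock in 4.4 is a further mismatch.

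Few patients are likely to be affected, and no power, sample-size or response-rate figure changes. What depends on the answer is the safety handling of those patients, the futibatinib discontinuation counts and the classification of deviations. This review takes no position on which limit is right.

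**What to change.** The sponsor should reconcile Protocol 5.3.1, 4.4, Table 5 and the Note below it in one clarifying amendment that:

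- states the event from which each limit is counted, including Table 5's 4 weeks;
- states which passage governs eye toxicity, and whether the Note operates within or outside the general limit;
- aligns 5.3.1 with 4.4, or explains why their 21-day limits start at different points.

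The choice of limit is a clinical decision for the sponsor. The cost is a short text amendment in four linked places. It changes no sample size and no analysis method. Until it is made, deviation reviewers need a documented statement of which passage applies, so that a site is not cited for following the other one.

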5.3.1.1. Futibatinib Dose Modifications for Nonhematologic Toxicities

Dosing modification guidelines for nonhematologic and eye toxicities are provided in [Table 4](#) and [Table 5](#), respectively.

Table 4: Dose Modifications for Related Nonhematologic Toxicities

Grade	Dose Interruption/Resumption	Dose Adjustment
Grade 1 or 2	Maintain treatment at the same dose level	None
Grade 3	Withhold treatment until return to baseline or Grade ≤ 1	Reduce by 1 dose level from the previous level, except for Grade 3 nausea and/or vomiting controlled by aggressive antiemetic therapy or Grade 3 diarrhea responsive to antidiarrheal medication which does not require a dose hold or reduction.
Grade 4	Discontinue treatment	Permanent discontinuation of futibatinib.
Grade 4 (lab abnormality AE)	Withhold treatment until return to baseline or Grade ≤ 1	Futibatinib will be permanently discontinued if assessed by the Investigator as life threatening. If it is in the best interest of the patient to continue treatment in the opinion of the Investigator and after discussion with the Sponsor, the patient can continue treatment at a reduced dose level. However, futibatinib should first be held until toxicity returns to baseline or Grade ≤ 1 .

Abbreviations: AE=adverse event; ALT=alanine aminotransferase; AST=aspartate aminotransferase.

Note: Interrupt futibatinib if any toxicities are intolerable, regardless of the grade (including Grade 1 and 2). If or when the toxicity resolves to a tolerable state, consideration can be given to resuming futibatinib at the same dose if deemed appropriate or reduced by one dose level if needed.

Table 5: Dose Modifications for Related Eye Toxicities

Grade and Definition	Study Drug Management
Grade 1	
If there is no evidence of eye toxicity on ophthalmologic examination, continue futibatinib therapy at the same dose level.
 
If diagnosis from ophthalmologic examination is keratitis or retinal abnormality such as central serous retinopathy (CSR)/ retinal pigment epithelial detachments (RPED), withhold futibatinib until signs and symptoms have resolved.
 
If toxicity is reversible (complete resolution or stabilization and asymptomatic) in 4 weeks according to ophthalmologic examination, resume futibatinib therapy at the next lower dose level after consultation with the medical monitor.
 
Monitor for recurrence every 1 to 2 weeks for a month and as clinically appropriate thereafter. If there is no recurrence then re-escalation can be considered in consultation with the medical monitor.^a

Grade 2	
Withhold futibatinib therapy.
 
If there is no evidence of drug-related corneal or retinal pathology on ophthalmologic examination, withhold futibatinib until signs and symptoms have resolved. Resume futibatinib therapy at the next lower dose level.
 
If diagnosis from ophthalmologic examination is keratitis or retinal abnormality, withhold futibatinib until signs and symptoms have resolved or stabilized.
 
If toxicity is Grade 2 and reversible (complete resolution or stabilization and asymptomatic) within 4 weeks according to ophthalmologic examination, resume futibatinib therapy at the next lower dose level after consultation with the medical monitor.

Grade 3	
If the toxicity is Grade 3, report as a serious adverse event and permanently discontinue futibatinib. If, however, the toxicity is Grade 3 and reversible (complete resolution or stabilization and asymptomatic) within 4 weeks and the subject is having clinical benefit, and the Investigator and the Sponsor's medical monitor agree that re-starting drug is in the best interest of the subject, then futibatinib therapy may be resumed at 2 dose levels lower if appropriate.^a Monitor for recurrence using appropriate investigations every 1 to 2 weeks for a month and as clinically appropriate thereafter.
 
For cases of recurrence consider permanent discontinuation.

Grade 4	
Permanently discontinue treatment with futibatinib.
 
Report as a serious adverse event and monitor resolution of the event until complete resolution, stabilization, or the subject is lost to follow-up or withdraws consent (which ever happens first).

Note: If a patient has been deriving benefit from treatment, and the Investigator can demonstrate that re-introduction of study drug is in the best interest of the patient considering the terminal nature of the disease, the drug may be re-introduced at a lower dose and/or intensity if the medical monitor is in agreement with this assessment. With appropriate re-consenting, the patient can be retreated with a 1- or 2-dose level reduction as appropriate, along with appropriate clinical follow-up as designated by the Investigator. The Investigator should also have the patient re-consent, explaining that re-introduction of study drug could lead to increased risk of recurrence.

Recommendations for hyperphosphatemia management are provided in [Table 6](#). These guidelines are based on emerging data from studies evaluating *FGFR* inhibitors, and from the experience of Investigators participating in ongoing studies of futibatinib. In addition, please see [Appendix B](#) for dietary guidelines for the treatment of hyperphosphatemia.

Table 6: Recommendations for Hyperphosphatemia Management

Serum Phosphorus Result ^a (mg/dL and mmol/L) ^b	Grade ^c	Futibatinib Dose Interruption and Modification Recommended Phosphate Binder for Management of Hyperphosphatemia ^d
ULN < P < 5.5 (mg/dL) ULN < P < 1.78 (mmol/L)	Grade 1	No interruption, consider phosphate binder once serum phosphorus level is > ULN. Should serum phosphorus level rapidly increase within 1 week, consider early phosphate-lowering therapy; eg, Sevelamer tablets 800 mg three times per day [TID]. Re-assess serum phosphate within 7 days.
5.5 ≤ P ≤ 7.0 (mg/dL) 1.78 ≤ P ≤ 2.26 (mmol/L)	Grade 2	No interruption, implement phosphate binder (monotherapy or in combination), Start with Sevelamer monotherapy (range from 800 mg TID to 2400 mg TID). Re-assess serum phosphate within 7 days. Escalate Sevelamer or add treatment with acetazolamide 250 mg QD or TID and/or lanthanum carbonate (Fosrenol®) 1.0 g QD or TID, and further titration, ^e if phosphate level continues to increase.
7.0 < P ≤ 10.0 (mg/dL) 2.26 < P ≤ 3.23 (mmol/L)	Grade 3	Dose reduce futibatinib to the next lower dose level and intensify phosphate lowering therapy. If the serum phosphorus level has resolved to ≤ Grade 2 within 14 days after dose reduction, continue futibatinib at the reduced dose level. Re-assess serum phosphate within 7 days and at least once a week. If the serum phosphorus level has not resolved to ≤ Grade 2 after 14 days, further reduce futibatinib from the last reduced dose level (or no lower than 12 mg QD). If the serum phosphorus level has not resolved to ≤ Grade 2 after 14 days of the second dose reduction of futibatinib (or no lower than 12 mg QD), interrupt dosing with futibatinib until it is resolved to ≤ Grade 2 before resuming futibatinib at the reduced dose prior to dose interruption.
P > 10.0 (mg/dL) P > 3.23 (mmol/L)	Grade 4	Interrupt futibatinib until it has resolved to ≤ Grade 2, then resume futibatinib at the next lower dose level and intensify phosphate lowering therapy. Re-assess serum phosphate within 7 days and at least once a week. If after 2 dose interruptions and 2 dose reductions the serum phosphorus level has not resolved to ≤ Grade 2 after 14 days, permanently discontinue futibatinib.

Abbreviations: P=phosphorus; QD=once a day; TID=three times a day; ULN=upper limit of normal

^a Serum phosphorus will be tested 4 days (± 24 hours) after Day 1 of Cycle 1 to initiate early intervention for hyperphosphatemia if indicated.

^b mmol/L=mg/dL x 0.3229 (conversion factor)

^c This grading for the range of serum phosphorus levels will be used for the protocol.

^d Phosphate binders can be used as monotherapy or in combination. Please consult the drug package insert. Sevelamer should be preferably taken in the middle of meals, both tablets and powder, in order to improve gastrointestinal tolerance and compliance. If Sevelamer cannot be used, other phosphate binders or hyperphosphatemia treatment drugs can be used. Lanthanum carbonate should be taken instead just after meals—tablets of Fosrenol® are quite big, but can be cut if required. No dose adjustments are needed in patients with renal or hepatic impairment.

^e Titrate the dose every 2-3 weeks until an acceptable serum phosphate level is reached.

